## **Research programme**

(i) Proposed research methodology, technical programme and feasibility analysis.

1 Research Methodology and Technical Programme

1.1 Research methods

In this project, 4D Label-free proteomics technology is applied, and the signal ratio (Ratio) of serum proteins in the treatment and control groups is used to measure the difference in their expression in different states, and the significance test T-test p value is calculated from the results of multiple repetitions of the experiment. when the Ratio is greater than the specified threshold and the p value is less than 0.05, the corresponding proteins can be considered to have significant differences in expression. the difference in expression of the corresponding protein can be considered significant. Then, the identified serum proteins were subjected to functional module analysis, clustering and then functional enrichment. The results of the analysis were more intuitive and detailed, and the functional correlation of the differentially expressed proteins in the comparative groups was found, and the expected related pathways were uncovered. Finally, PRM technology is applied to validate the candidate proteins and confirm their reproducibility and reliability as clinical biomarkers.

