1.3 Inclusion criteria

Inclusion criteria

(1) Meet the diagnostic criteria for ischemic stroke in the Chinese Guidelines for Diagnosis and Treatment of Acute Ischemic Stroke 2018.

(2) Comply with the diagnostic criteria for ischemic stroke in TCM.

(3) Within 2 weeks of acute onset of ischaemic stroke.

(4)  $4 \leq \text{NIHSS score} < 15$ .

(5) Age 40-80 years old.

Exclusion criteria

 Diagnosis of haemorrhage or other pathological brain diseases based on head CT or MRI;

(2) Allergy, allergy to the test drug or its related flavour or ingredients;

(3) Age <40 years or >80 years;

(4) Severe hepatic or renal impairment.

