1.5 Specific experimental steps

(1) Extraction of sample whole protein: extract sample whole protein using protein lysate, protease/modification inhibitor, ultrasonic crushing, high-speed centrifugation;

(2) Protein extraction quality control: use SDS-PAGE, BCA, Bradford and other methods to do preliminary analysis of the extracted sample proteins, in order to assess the parallelism between the samples, the presence of high abundance of proteins, the presence of protein degradation phenomenon, the protein concentration to meet the subsequent experiments and so on;

(3) Proteolysis: After the extracted proteins are deformed and reduced, trypsin is used to enzymatically digest the proteins to obtain peptide samples;

(4) Enrichment of modified peptide fragments: enrichment of modified peptide fragments in peptide samples with antibodies specific for the purpose of modification;

(5) Separation of peptide fractions: Using high performance liquid chromatography (HPLC) or enriching peptides obtained by enzymatic digestion or modified antibodies, peptide fractions are separated according to their abundance, in order to reduce the complexity of the sample and improve the sensitivity of mass spectrometry detection;

(6) Liquid-mass spectrometry analysis: The enriched peptide samples were analysed by Orbitrap Exploris 480 liquid-mass spectrometer to obtain raw data containing primary and secondary spectra;

(7) Spectrogram search data analysis: peptide samples containing modified peptides were identified and quantitatively analysed using Maxquant, Mascot and Proteome Discoverer software; (8) Bioinformatics analysis.

2 Feasibility analysis:

(1) Novel topic selection: This project adopts 4D Label-free proteomics technology and PRM technology to elucidate for the first time the mechanism of action and potential targets of Chuanhong Zhongfeng Capsule in the treatment of acute cerebral infarction, to provide a prospective basis for the precise medical treatment of this disease, and to provide a research direction for the prevention and treatment of cerebral infarction by traditional Chinese medicine compound. Therefore, this topic is feasible in terms of topic selection and theory.

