This study is the first to investigate the mechanism of action and potential targets of Chuanhong Zhongfeng Capsule in the treatment of acute cerebral infarction by using 4D Label-free proteomics technology and PRM technology.

(III) Annual programme progress and expected goals.

('Starting and ending years' are counted from the date of application, and the completion period is generally no more than 3 years).

First year/annual plan: collect patients for clinical enrolment and improve the study protocol.

Expected goal: Improve the study protocol and complete the collection of patient blood samples.

Year 2/annual plan: complete QC and total protein extraction, start mass spectrometry and raw letter analysis.

Expected goal: Proteomics data analysis.

Third year/annual plan: conduct PRM validation, article writing and report project summary report.

Expected goal: complete 1 SCI and 1 core journal paper.

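### Does leaving the unit of the t-test unnamed allow repeat assay runs to be counted as independent patients?

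*SAP*

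**What the plan says.** The only inferential rule in the SAP is in section 1.1. The contrast is between arms: "the signal ratio (Ratio) of serum proteins in the treatment and control groups is used to measure the difference in their expression". The test is described by "the significance test T-test p value is calculated from the results of multiple repetitions of the experiment", and a protein is declared different "when the Ratio is greater than the specified threshold and the p value is less than 0.05". The threshold has no value, and the SAP gives no group size, no number of runs per sample and no variance.

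Two other places bear on what a repetition is. Section 1.5 lists the laboratory work from protein extraction to database search, and includes a quality-control step done "in order to assess the parallelism between the samples". Part (III), on annual progress, sets the first-year goal as improving the study protocol and to "complete the collection of patient blood samples". No section mentions duplicate injections, technical replicates or pooling.

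After the differential-expression rule come module analysis, clustering and enrichment. The sequence ends with a targeted assay: "Finally, PRM technology is applied to validate the candidate proteins".

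**The concern.** Treatment is given to patients, so the patient is the independent unit. Repeat runs of one serum share that patient's biology and are strongly correlated. If they enter a two-sample t-test as separate observations, the standard error is too small and the 0.05 condition is too easy to meet.

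The wording gives some ground for that reading. The heading "1.5 Specific experimental steps" covers laboratory procedures only, so repeating the experiment could be taken as repeating the assay. The candidate list would then hold too many false proteins, and the targeted assay, which comes last, could not keep them out of the enrichment results.

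A lesser point is that the plain t-test ignores entry NIHSS, age and time from onset. All three must be known at enrolment; for example, eligibility requires "Within 2 weeks of acute onset of ischaemic stroke".

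**Working it through.** **Is there a figure to reproduce?** No. The SAP states no sample size, power or variance. The 0.05 is a chosen cut-off.

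**Inputs.** From section 1.1: p < 0.05 (taken as two-sided) together with a Ratio threshold. Assumed, because the SAP gives none of them: m = 2 or 3 runs per patient; ICC (share of variance between patients) 0.7-0.9; n = 10-30 patients per group; log2 SD of a single run 0.5 or 0.8; threshold 1.2- or 1.5-fold in either direction, that is 0.263 or 0.585 on the log2 scale.

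**Step 1: t-test alone.** The design effect is DE = 1 + (m − 1) × ICC, and the true level when runs are counted is 2 × [1 − Φ(1.96/√DE)].

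- m = 1: DE = 1, level 0.05. The two readings coincide.
- m = 2: DE = 1.7 to 1.9, level 0.133 to 0.155 (simulated 0.136-0.169).
- m = 3: DE = 2.4 to 2.8, level 0.206 to 0.241 (simulated 0.207-0.262). The standard error is understated by 1 − 1/√2.4 = 35% to 1 − 1/√2.8 = 40%.
- Runs averaged within patient: simulated 0.047-0.054.

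**Step 2: the SAP's actual rule, threshold and p < 0.05 together.** Simulated false-call rates with 3 runs; each range covers ICC 0.7 to 0.9:

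| Threshold | log2 SD | n per group | Runs counted | Runs averaged |
|---|---|---|---|---|
| 1.5-fold | 0.5 | 10 | 0.004-0.007 | same |
| 1.5-fold | 0.8 | 20 or 30 | under 0.02 | same |
| 1.2-fold | 0.5 | 30 | 0.024-0.035 | 0.023-0.033 |
| 1.5-fold | 0.8 | 10 | 0.069-0.090 | 0.043-0.044 |
| 1.2-fold | 0.8 | 30 | 0.156-0.187 | 0.050 |
| 1.2-fold | 0.5 | 10 | 0.178-0.209 | 0.049 |
| 1.2-fold | 0.8 | 10 | 0.217-0.259 | 0.049-0.050 |

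The pattern can be checked by hand.

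- *Threshold decides.* At n = 30, SD 0.5, ICC 0.9, a patient's mean of 3 runs has SD 0.5 × √(0.9 + 0.1/3) = 0.483. The standard error of the group difference is 0.483 × √(2/30) = 0.125, and the smallest significant difference is about 2.00 × 0.125 = 0.250. This is below 0.263, so the threshold settles nearly every call and counting runs hardly matters.
- *p value decides.* At n = 10, SD 0.8, the run-level standard error is 0.8 × √(2/30) = 0.207, and the smallest significant difference is about 2.00 × 0.207 = 0.413. This is above 0.263, so the threshold gives no protection and the full t-test inflation appears: 0.259/0.050 = 5.2 times.

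**Step 3: does the SAP describe repeat runs?** Section 1.5 is one sequence: extract, check, digest, enrich, separate, run, search. Its quality check compares samples with one another, not runs of one sample. Part (III) collects blood from patients, and section 1.1 compares treatment with control. Carrying out the sequence on the next patient's serum is also a repetition of the experiment. Nothing in the text supplies an m above 1.

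**Step 4: covariates.** With k = 3 terms, the efficiency relative to the t-test is 1/[(1 − R²)(1 + k/(2n − k − 3))].

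- n = 10: 1/(0.9 × 1.214) = 0.92 at R² = 0.1; 1/(0.6 × 1.214) = 1.37 at R² = 0.4.
- n = 30: 1/(0.9 × 1.056) = 1.05 at R² = 0.1; 1/(0.6 × 1.056) = 1.58 at R² = 0.4.

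The sign of the gain depends on n and R², and the SAP gives neither.

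**The case for a change.** The strongest case for a change is that the unit of analysis belongs in a SAP, so the absent protocol does not excuse the gap. The SAP does say what feeds the t-test, in words that do not identify the unit. Its own use of experimental leans towards the laboratory, and a single sentence would close the gap without new data. The Ratio threshold cannot be relied on as protection, since its value is not given.

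Part of this stands. The definition is unwritten, the laboratory reading is possible, and the inflation figures are right for the case they describe.

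The rest is weaker. The harm needs repeat runs per patient, which the SAP never mentions, and an analyst who then ignores the pairing of runs within patients. One word in roughly translated English is thin evidence for either. The argument from the order of steps is also unsettled: section 1.1 first sends the identified proteins into module analysis and enrichment, and only afterwards speaks of differentially expressed ones, so it is unclear whether the p value decides what enters that stage. The biomarker claim itself is made only after the targeted assay.

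**Conclusion.** No change to the plan follows. The SAP leaves a repetition undefined, but its described workflow and material fit one value per patient at least as well as repeat runs. On that reading the t-test holds its 5% level. If serum is in fact run more than once, averaging within patient is what a competent analyst would do, and it also gives 5%.

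The damage arises only if runs exist and are counted as independent. Under the SAP's joint rule it then ranges from none to about fivefold. That range rests on assumed values for run count, ICC, group size, SD and threshold, so it does not show that the plan's rule gives a wrong answer.

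The missing covariates are a matter of precision, not validity. Adjustment loses about 8% efficiency at 10 per group with R² = 0.1 and gains at larger n or R², which makes the plain t-test a fair trade-off.

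### Proteins are declared significant at an unadjusted t-test p < 0.05 plus a Ratio cut with no stated value, so the false-positive share of the list is not controlled

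*SAP*

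**What the plan says.** SAP section 1.1 describes the between-group comparison: "the signal ratio (Ratio) of serum proteins in the treatment and control groups is used to measure the difference in their expression". For each protein, "the significance test T-test p value is calculated from the results of multiple repetitions of the experiment". The declaration rule has two parts. A protein qualifies "when the Ratio is greater than the specified threshold and the p value is less than 0.05", and then "the corresponding proteins can be considered to have significant differences in expression".

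The threshold is called specified, but no value appears in the SAP. No false discovery rate, q-value, Bonferroni or permutation step is named. The bioinformatics step that ends the list in section 1.5 is only a label.

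Functional module analysis, clustering and enrichment come next in section 1.1, with the aim of finding functional links among the differentially expressed proteins and the pathways involved. The last step is PRM: "Finally, PRM technology is applied to validate the candidate proteins and confirm their reproducibility and reliability as clinical biomarkers". The timetable under (III) Annual programme progress and expected goals puts it in the last year: "Third year/annual plan: conduct PRM validation, article writing and report project summary report". The SAP states neither the samples PRM will use nor what counts as passing.

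**The concern.** A label-free serum experiment tests many proteins at once. With a per-protein level of 0.05, about 5% of the unchanged proteins reach p < 0.05 by chance. If few proteins truly change, those chance hits can outnumber the real ones. The Ratio cut removes some of them, but it is a filter and not error-rate control. How much it removes depends on the cut, the number of patients and the variability, and the SAP fixes none of these.

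The declared list carries the study's stated aim of mechanism and potential targets. Pathways are read from the differentially expressed proteins before PRM. With the cut left open, it could also be chosen after the data are seen, which would change both the length of the list and its reliability.

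**Working it through.** The SAP gives no sample size, power, number of proteins or false discovery level, so there is no derived figure to reproduce. The only numerical input it supplies is p < 0.05. Everything else below is an assumption.

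**Step 1: p < 0.05 alone.** With m proteins tested, a fraction π truly changed and power w:

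- Expected false positives = 0.05 × m × (1 − π). If nothing changes, this is 15 for m = 300, 25 for 500, 50 for 1000 and 100 for 2000.
- False share = 0.05(1 − π) / [0.05(1 − π) + wπ]. With π = 0.05 and w = 0.8: 0.0475 / (0.0475 + 0.0400) = 54%. At the same power it is 75%, 36% and 20% for π = 0.02, 0.10 and 0.20. It does not depend on m.

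**Step 2: the Ratio cut added.** Assumptions: two-sample t-test on log2 values with one value per patient; 10, 20 or 30 patients per group; log2 SD 0.4, 0.6 or 0.8; 5% of proteins changed by log2 0.8 (1.74-fold); cut applied in both directions. Let a and b be the probabilities that an unchanged and a changed protein meet both conditions, from 400,000 simulated proteins of each kind per setting. False share = 0.95a / (0.95a + 0.05b).

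| Patients per group | log2 SD | 1.2-fold | 1.5-fold | 2-fold |
|---|---|---|---|---|
| 10 | 0.4 | 48% | 2% | 0% |
| 10 | 0.6 | 55% | 39% | 2% |
| 10 | 0.8 | 63% | 61% | 25% |
| 20 | 0.4 | 39% | 0% | 0% |
| 20 | 0.6 | 49% | 4% | 0% |
| 20 | 0.8 | 52% | 32% | 0.5% |
| 30 | 0.4 | 17% | 0% | 0% |
| 30 | 0.6 | 48% | 0.3% | 0% |
| 30 | 0.8 | 49% | 9% | 0% |

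**Step 3: why the cut sometimes does nothing.** At an SD equal to the assumed value, the smallest fold change that reaches p < 0.05 is 2^[t(0.975, 2n − 2) × SD × √(2/n)]. For n = 20 this is 1.19 at SD 0.4 and 1.43 at SD 0.8. For n = 10 and SD 0.8 it is 1.68. A 1.2-fold cut removes almost nothing there, because significant proteins already exceed it.

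**Step 4: Benjamini-Hochberg at 5% added.** 500 proteins, 25 of them changed, 1.5-fold cut, 400 runs, average counts:

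| Setting | Raw p: true + false (false share) | Adjusted p: true + false (mean false share) |
|---|---|---|
| n = 20, SD 0.8 | 20.0 + 9.5 (32%) | 8.9 + 0.46 (4%) |
| n = 10, SD 0.8 | 13.9 + 21.8 (61%) | 0.8 + 0.09 (4%) |
| n = 30, SD 0.4 | 24.5 + 0 | 24.5 + 0 |

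Over all 27 combinations of n, SD and cut, the mean false share with adjustment was at most about 5%.

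**The case against.** The strongest reply is that this is a two-stage discovery design. The SAP calls the selected proteins candidates and leaves their reliability as biomarkers to PRM, so a lenient first screen can be legitimate. That is fair for choosing what goes to PRM. It does not cover calling the proteins significantly different, or interpreting their pathways before PRM. Nor does the SAP say that PRM uses new patients; re-measuring the same samples would confirm the assay and not the group difference.

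Four further points limit the size of the finding:

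- **Direction of the cut.** The SAP says only greater than the threshold. If only increases count and all true changes are increases, 63% becomes 46% (n = 10, SD 0.8, 1.2-fold) and 32% becomes 19% (n = 20, SD 0.8, 1.5-fold). If true changes split evenly by direction, the shares do not move.
- **Many settings are harmless.** In 13 of the 27 settings the false share is already 5% or less without adjustment. A strict cut with low variability can suffice.
- **A rough bound exists afterwards.** Given the numbers tested and declared, a reader can cap the expected false count at 0.05 times the number tested. What is missing is a level fixed in advance.
- **Reach into the enrichment.** Section 1.1 applies clustering and enrichment to the identified proteins and names the differentially expressed ones only in the next sentence, so how far false positives carry into that step is not certain.

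All four stand as limits. None supplies the missing error control or the missing number.

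**Conclusion.** The concern holds. As written, the rule declares significance on an unadjusted p value and an unquantified Ratio cut, so the false-positive share of the declared list is not controlled. Under the assumptions above it ranges from about 0% (strict cut, low variability) to just over 60% (loose cut, high variability, 10 per group). The claim is that the share is not fixed in advance, not that it is always high; its size rests on the assumed number of patients, SD, effect, fraction changed and cut. PRM is a partial safeguard for the final candidates but does not protect the list interpreted before it. This should be fixed before the mass-spectrometry data are analysed, which the timetable places in the second year.

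**What to change.** Replace the rule in section 1.1 with: a protein is differentially expressed if its Benjamini-Hochberg adjusted p value, over all proteins quantified in the comparison, is below 0.05 and its fold change passes the pre-stated numerical threshold in either direction. Write that threshold into the SAP before the mass-spectrometry data are analysed. Report raw and adjusted p values. List proteins that meet only raw p < 0.05 as exploratory candidates, still eligible for PRM but not called significant. It would also help to state which samples PRM uses and what counts as passing.

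The cost is SAP wording and one line of code, plus a shorter declared list. With 500 proteins, 25 of them changed, and a 1.5-fold cut, 20 per group at SD 0.8 goes from about 20 true and 9.5 false to about 9 true and 0.5 false. With 10 per group the loss depends on variability: about 19 of the 25 are still declared at SD 0.4, about 4 at SD 0.6 and fewer than 1 at SD 0.8. With 30 per group and SD 0.4 nothing changes. The exploratory list keeps the remaining candidates available for PRM.

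### The rule for declaring a protein differentially expressed has only an upper Ratio bound and no named numerator, so as written it can declare change in one direction only

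*SAP*

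**What the plan says.** SAP section 1.1 (Research methods) holds the document's only rule for selecting proteins. It introduces the measure thus: "the signal ratio (Ratio) of serum proteins in the treatment and control groups is used to measure the difference in their expression in different states". Both groups are named, but neither is made the numerator.

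The decision rule follows. A protein is selected "when the Ratio is greater than the specified threshold and the p value is less than 0.05", and then "the corresponding proteins can be considered to have significant differences in expression". The threshold has no value in this document and the inequality runs one way. The p value comes from a t-test whose sidedness is not stated. No section gives a reciprocal cut-off, an absolute log ratio or a larger-over-smaller ratio.

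The same section describes the later steps without naming a direction: "the functional correlation of the differentially expressed proteins in the comparative groups was found", and finally "PRM technology is applied to validate the candidate proteins". Under 2 Feasibility analysis the project is to "elucidate for the first time the mechanism of action and potential targets of Chuanhong Zhongfeng Capsule in the treatment of acute cerebral infarction"; 3 Innovative points repeats that aim. None of these statements is limited to raised or to lowered proteins.

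**The concern.** A fold-change filter meant to find differences needs two bounds: one for proteins that are higher in the treatment group and one for proteins that are lower. The SAP states only the upper one. Because the numerator is open as well, a reader cannot tell which direction the literal rule would drop.

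The differential list and the candidates taken from it to PRM are at stake. A drug can act by lowering a protein as well as by raising one, and the SAP's aims cover both. The functional analysis is affected in so far as it rests on the differential list; section 1.1 also speaks of analysing the identified proteins as a whole, and that part would not be touched.

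The wording also allows three readings (treatment over control, control over treatment, larger over smaller) that give different lists. If the choice stays open until the data are seen, the rule is not fully pre-specified.

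**Working it through.** The SAP gives no sample size, standard deviation or threshold value, so it has no figure to reproduce. The check is on the logic of the rule.

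**Inputs from SAP section 1.1:** Ratio R of the two groups, numerator unstated; select if R > c and p < 0.05.

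**Assumption:** R is directional and c ≥ 1.

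**Step 1, rule as written.** If c ≥ 1, then R > c implies R > 1. By contraposition, R < 1 implies that the protein is not selected. The p value does not enter, and neither do sample size or variability.

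**Step 2, dependence on the numerator.** Take two proteins, both with p < 0.05: A with treatment/control = 2 and B with treatment/control = 0.5. Use c = 1.5 for illustration; any c from 1 to just below 2 gives the same pattern.

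| Reading of Ratio | Protein A | Protein B |
|---|---|---|
| treatment/control | 2 > 1.5, declared | 0.5 < 1.5, not declared |
| control/treatment | 0.5 < 1.5, not declared | 2 > 1.5, declared |
| larger/smaller | 2 > 1.5, declared | 2 > 1.5, declared |

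One rule gives three different lists. Only the third matches a conclusion that names no direction, and the SAP does not state it.

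**Step 3, a threshold below 1 is no way out.** With c = 0.5, R = 0.67 passes because 0.67 > 0.5, but R = 0.4 fails because 0.4 < 0.5. The strongest decreases are still excluded. R = 1 also passes, so the cut-off no longer screens out small changes.

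**Step 4, the rule with a reciprocal bound.** Select if R > c or R < 1/c, and p < 0.05. Replacing R by 1/R gives 1/R > c or 1/R < 1/c, that is R < 1/c or R > c, which is the same set. The list no longer depends on the numerator. For c ≥ 1 the rule is also identical to larger/smaller > c.

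**Step 5, cost under no true difference.** If the log ratio is distributed symmetrically about zero, the two tails are equally likely: P(R > c and p < 0.05) = P(R < 1/c and p < 0.05). Counting both tails therefore doubles the false flags. At c = 1 with a two-sided test, these are 0.05/2 = 2.5% for the one-directional rule and 5% for the two-directional rule. Per 1000 unchanged proteins (an assumed number) that is 1000 × 0.025 = 25 against 1000 × 0.05 = 50. A larger c lowers both figures and leaves their ratio at two.

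**The case against.** The strongest reply is that the harm needs a reading that section 1.1 itself counts against. The Ratio is said to measure a difference, the conclusion speaks of differences, and the later steps concern differentially expressed proteins without a direction. The natural intent is a fold-change cut-off either way, loosely expressed. The document is a research-programme text with signs of rough translation. Its definite wording about the threshold may point to a protocol that is not shown, and the programme plans protocol work in the first year, before mass spectrometry in the second.

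Much of this stands. A reader might infer that lowered proteins will be ignored in this trial; the documents do not support that, because the surrounding text points to both directions. A reader might also want a percentage of true changes lost. None can be given from the documents: any detection rate would rest on an assumed sample size, standard deviation and threshold, and would say nothing about how likely the literal reading is. Nor do the documents show that the rule needs a log scale to get the direction right; that is a convenience and not part of the error. It is also true that the intensities are measured in any case, so nothing is lost irreversibly.

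The reply does not remove the misstated inequality. This is a decision rule that the SAP does state, not a detail it merely leaves out, and applied as written it conflicts with the conclusion in its own sentence.

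**Conclusion.** The concern holds as a misstated selection rule. With a directional Ratio and a threshold of at least 1, the rule in SAP section 1.1 can never declare a protein with an observed Ratio below 1. The size is all or nothing: one direction is excluded entirely, whatever the sample size, variability or p value, and which one depends on a numerator the SAP does not name. The result rests on those two conditions alone; a larger-over-smaller ratio would avoid it, but the text states none.

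It does not follow that the analysis will be one-sided in practice, and no quantified loss of true findings can be claimed. The point is worth correcting before analysis, because the differential list feeds the PRM candidates and the correction is short.

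**What to change.** Replace the rule in section 1.1 with wording such as: Ratio is the signal in the treatment group divided by the signal in the control group; a protein is differentially expressed if Ratio > c or Ratio < 1/c, and the two-sided t-test has p < 0.05. Fix c as a number before mass spectrometry data are available, or cite the place where it is already fixed. Report raised and lowered proteins separately. If a larger-over-smaller ratio was meant, say so; for c ≥ 1 it is the same rule. Computing Ratio and test on the same log2 scale makes the two bounds symmetric (|log2 Ratio| > log2 c), but this is optional.

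The cost is wording only, with no extra samples or assays at the discovery stage. The downside is that false flags among unchanged proteins roughly double relative to the one-directional rule, so more candidates may reach PRM unless the p values are adjusted for multiplicity.
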